Use of an Independent Data Monitoring Committee, Dose Escalation Committee, or similar review group	NO

A total of 440 participants are planned to be enrolled. At the time of inclusion, participants will be screened for SARS-CoV-2 seropositivity status and stratified according to age. Those who are seronegative will be randomized as shown in [Table 4.2](#).

As a precautionary step, a Sentinel Safety Cohort of 6 participants (younger adults only) within each dosing group from Cohort 1 will be enrolled. An Early Safety Data Review (ESDR) will be performed, including evaluation of safety data and laboratory measures to D09 in Cohort 1 among younger adults 18-49 years of age. Upon acceptable safety demonstrated from unblinded data review by limited members of the Sponsor Study Team (RMO, Biostatistician and Programmer, Pharmacovigilance Science Expert, and Global Safety Officer), the remaining participants in Cohort 1 and all participants in Cohort 2 will be enrolled. Further details are provided in [Section 8.4](#).

Table 4.2: Planned sample size

Participants 18-49 years of age					
Cohort	Group	Dose Level*	Adjuvant	N	
				Sentinel Safety† (N=30)	Total (N=300)
Cohort 1: 1 injection	1	5 µg	AF03	6	20
	2	5 µg	AS03	6	20
	3	15 µg	AF03	6	20
	4	15 µg	AS03	6	20
	5	Placebo	None	6	20
Cohort 2: 2 injections	6	5 µg	AF03	N/A	20
	7	5 µg	AS03	N/A	60
	8	15 µg	AF03	N/A	20
	9	15 µg	AS03	N/A	60
	10	15 µg	None	N/A	20
	11	Placebo	None	N/A	20
Participants 50 years of age and older					
Cohort	Group	Dose Level*	Adjuvant	N (N=140)	
Cohort 1: 1 injection	1	5 µg	AF03	10	
	2	5 µg	AS03	10	
	3	15 µg	AF03	10	
	4	15 µg	AS03	10	
	5	Placebo	None	10	
Cohort 2: 2 injections	6	5 µg	AF03	10	
	7	5 µg	AS03	30	
	8	15 µg	AF03	10	
	9	15 µg	AS03	30	
	10	15 µg	None	N/A‡	
	11	Placebo	None	10	

*Antigen Formulation naming for each dose level: CoV2 preS dTM antigen: Formulation 1 (low-dose [5 µg]); Formulation 2 (high-dose [15 µg])

† Sentinel Safety Cohort: 6 participants within each dosing group from Cohort 1 (18-49 years of age only) will be included in the Sentinel Safety Cohort.

‡ As part of risk mitigation for enhanced COVID-19, the older age stratification (≥ 50 years) will not be allocated to this study arm.

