The study will be conducted in adults 18 years of age and older. Clinical and epidemiological data from the COVID-19 pandemic have consistently indicated a higher risk of severe complications and death in older adults (35) (36). Therefore, it is considered of great relevance to generate data in the older adult population to inform schedule and formulation selection that will serve the general adult population, including those at particular risk of poor outcomes. A Sentinel Safety Cohort among younger adults is included to provide preliminary short-term safety data prior to enrollment of older adult participants. The study incorporates several measures to mitigate the theoretical risk of vaccine-associated ERD. These include a higher representation of the younger adult strata for the same reason, given that adults over 50 years of age have also been overrepresented in studies describing critical illness and death, although to a lesser degree than those older than 75 years (35). Therefore, the proposed design aims at generating data that will allow selection of the relevant formulations and injection schedule accounting for potential age

effects. Data for each formulation will be generated in both younger adults and older adults, allowing the evaluation of the consistency in the patterns of immune response for each formulation between the 2 age strata; additionally, aggregated “main” effects by age will be evaluable by comparing pooled older adult data (n=120 across vaccine formulations) and pooled younger adult data (n=240 across vaccine formulations with corresponding data in the older strata).

Evidence to date indicates that individuals with chronic medical conditions are at increased risk of severe outcomes associated with COVID-19 (37). The exclusion of individuals with chronic underlying conditions is considered an additional risk mitigation measure to address the theoretical phenomenon of immune enhancement. Clinical and epidemiological data indicates that the overrepresentation of older adults among those with critical or fatal COVID-19 illness is meaningfully ameliorated when stratified/controlled for the presence of chronic medical conditions (26). Exclusion of individuals with chronic medical conditions from this trial mitigates the potential (theoretical) risk of exacerbating the occurrence of critical or fatal outcomes as a result of study participation.

Rationale for Active Arms

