The study aims at selecting schedule and formulation to progress to further clinical development. The importance of the schedule evaluation has been stated above, and it is the justification for inclusion of Cohort 1 and Cohort 2 in each age strata in the study. Within each cohort, the study design allows the evaluation of the candidate vaccine protein dose level (2 different dose levels) adjuvanted with AS03 or AF03. A range of dose level evaluation is of particular interest in the setting of a pandemic: if adequate responses are observed with lower doses of antigen, higher number of doses of vaccine could be supplied to address the anticipated large demand that will be needed to end the pandemic.

Within Cohort 2, the study includes an arm with the higher dose level of protein antigen alone (unadjuvanted). This arm allows the evaluation and demonstration of the expected adjuvant effects (magnitude and quality of the immune response and dose-sparing effect). While it is anticipated that an adjuvanted formulation will be optimal, this study design will allow the generation of empirical data supporting such assumption. The unadjuvanted arm is restricted to the younger adult stratum, as a risk mitigation measure: previous studies with SARS-CoV-1 inactivated and protein-based vaccines suggested the possibility of vaccine-induced immunopathology upon viral infection when used alone or with a Th2-based adjuvant (alum) (9). AS03 and AF03 adjuvants have been generally associated with a balanced Th1/Th2 immune response (10) (11). Exclusion of unadjuvanted arms from the older adult stratum mitigates the potential (theoretical) risk of vaccine-induced immunopathology occurring in those who are already at higher risk of more severe COVID-19 illness.

Rationale for Higher Sample Size for AS03 Cohort 2 Arms, and Rationale for Including AF03

Given the large clinical and post-marketing experience with AS03, in addition to its readiness for large-scale supply and the extensive and multi-national regulatory experience, higher priority will be given to AS03 adjuvanted formulations for advancement into Phase III development. Nevertheless, generating meaningful Phase I/II clinical data with AF03 adjuvanted formulations is still of interest for several reasons: 1) AF03 can serve as an alternative adjuvant system, should any issues arise during development with AS03; 2) the AF03 adjuvant may still allow to increase

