future supply, in the event supply beyond AS03 capacity is possible with the recombinant protein and needed to address the pandemic; 3) the AF03 adjuvant may be of interest in the future if COVID-19 becomes seasonal, in which case a co-formulated vaccine would be attractive; in such circumstances, co-formulation with AF03 will be more feasible than with AS03 as both protein and adjuvant are proprietary to Sanofi Pasteur. The higher priority given to AS03 adjuvanted formulations and the higher likelihood of robust immune responses with a 2-injection schedule provides rationale to generate more precise data for AS03 formulations in Cohort 2 of this Phase I/II study; this is the justification for a sample size of 90 across age groups for the AS03 adjuvanted arms in Cohort 2. All other arms in the study will have a size of 30 total, except for the un-adjuvanted arm which would only comprise 20 younger adults.

Rationale for Blinding

This is an observer-blind study for formulation and adjuvant. Owing to the need for mixing of study formulations from separately supplied antigen, adjuvants, and / or diluent, the person preparing and administering the vaccine will be unblinded to vaccine group assignment. Blinding of all “observers” will minimize the risk of bias arising from the possibility of consciously or unconsciously influencing the reporting of study outcome measures due and knowledge of the formulation administered.

Rationale for Placebo

Placebo, rather than a benefit licensed vaccine, will be used for comparison to vaccine to allow safety comparisons between vaccine and placebo as there are no other licensed COVID-19 vaccines on the market. The inclusion of placebo groups will also maintain the blind, allowing the unbiased evaluation of clinical outcomes related to COVID-19-like illness and SARS-CoV-2 infection by treatment group (secondary efficacy objective).

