9.2 Sample Size Determination

This is a first-in-human study to assess the safety profile and immune responses to different formulations of the study vaccine when compared to placebo. A total of 440 participants will be enrolled. No formal power calculation has been performed. The sample size was determined based on logistical considerations and common practices for first-in-human trials.

Vaccine arms will be aggregated to perform complementary assessments on the following main effects: age [(18-49 years [N=240], \geq 50 years [N=120]), dose (low [N=180], high [N=180]), injection schedule (1-injection [N=120], 2-injection [N=240]), adjuvant type (AS03 [N=240], AF03 [N=120]), overall adjuvant (high-dose with adjuvants [N=180], high-dose without adjuvants [N=20]), and dose-sparing adjuvant (low-dose with adjuvants [N=180], high-dose without adjuvants [N=20]).

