5.1.1.4 Statistical Methods for Primary Immunogenicity Objective

The primary endpoints for the evaluation of immunogenicity are based on neutralizing antibody titers, which will be measured with the neutralization assay. The statistical analyses will be performed for the following primary endpoints below on overall population and by age group:

1. Antibody titer on D01, D22, and D36
2. Fold-rise (fold-rise in serum antibody neutralization titer post-vaccination relative to D01) at D22, and D36
3. 2-fold and 4-fold rise in serum neutralization titer relative to D01 at D22, and D36
4. Occurrence of neutralizing antibody seroconversion, defined as baseline values below LLOQ with detectable neutralization titer above assay LLOQ at D22 and D36.

Vaccine arms will be aggregated to perform complementary assessments on the following main effects. The primary endpoints above will also be summarized for the main effects.

1. age [(18-49 years, \geq 50 years), where the category of 18-49 years (N=240) includes all vaccine arms except high dose no adjuvant arm aged 18-49 years old; the category of \geq 50 years (N=120) includes all vaccine arms aged 18-49 years old.]
2. dose (low, high), where the category of low (N=180) includes vaccine arms of low dose with either AF03 or AS03 adjuvant; the category of high (N=180) includes vaccine arms of high dose with either AF03 or AS03 adjuvant.
3. injection schedule (1-injection, 2-injection), where the category of 1-injection (N=120) includes vaccine arms in cohort 1; the category of 2-injection (N=240) includes vaccine arms in cohort 2 except the high-dose with no adjuvant arm.

4. adjuvant type (AS03, AF03), where the category of AS03 (N=240) includes vaccine arms with adjuvant AS03; the category of AF03 (N=120) includes vaccine arms with adjuvant AF03.
5. overall adjuvant (high-dose with adjuvants, high-dose without adjuvants), where the category of high-dose with adjuvants (N=180) includes vaccine arms of high-dose with either AS03 or AF03; the category of high-dose without adjuvants (N=20) includes the vaccine arm with high-dose and no adjuvant.
6. dose-sparing adjuvant (low-dose with adjuvants, high-dose without adjuvants); where the category of low-dose with adjuvants (N=180) includes vaccine arms of low-dose with either AS03 or AF03; the category of high-dose without adjuvants (N=20) includes the vaccine arm with high-dose and no adjuvant.

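### The pooled D36 adjuvant summaries (SAP 5.1.1.4 items 4 to 6) mix adjuvant with injection schedule; matched rows should be added beside the prespecified pools

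*SAP*

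**What the plan says.** Protocol 9.2 and SAP 5.1.1.4 pool vaccine arms into six complementary main effects and summarize the primary neutralization endpoints, including D36, for each. Three matter most here.

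- **Item 5, overall adjuvant.** The SAP says "the category of high-dose with adjuvants (N=180) includes vaccine arms of high-dose with either AS03 or AF03". Protocol 9.2 gives the same pairing: "overall adjuvant (high-dose with adjuvants [N=180], high-dose without adjuvants [N=20".
- **Item 6, dose-sparing adjuvant.** The low-dose adjuvanted arms (N=180) are paired with the same 20 unadjuvanted participants.
- **Items 3 and 4, schedule and adjuvant type.** Protocol 9.2 lists "injection schedule (1-injection [N=120], 2-injection [N=240]), adjuvant type (AS03 [N=240], AF03 [N=120".

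On the unadjuvanted arm, Protocol 4.2 says "Within Cohort 2, the study includes an arm with the higher dose level of protein antigen alone (unadjuvanted", and of its purpose: "This arm allows the evaluation and demonstration of the expected adjuvant effects". The footnote to Protocol Table 4.2 says the older stratum "will not be allocated to this study arm".

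SAP 5.1.1.4 gives results overall and by age group. It states no split by schedule for items 4 to 6. SAP Table 5.1 plans geometric means with 95% CIs and responder percentages with 95% CIs.

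**The concern.** Group 10 was placed in Cohort 2 so that adjuvanted and unadjuvanted antigen could be compared on the same schedule. Items 5 and 6 add one-injection participants to the adjuvanted side only. Protocol 4.2 expects schedule to matter, citing "the higher likelihood of robust immune responses with a 2-injection schedule". If that is right, the D36 pools understate the adjuvant and dose-sparing effects. In item 4, AS03 gains over AF03 merely because more of its participants have two injections.

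The documents take care over matching elsewhere. For the age comparison, Protocol 4.2 limits the younger pool to "n=240 across vaccine formulations with corresponding data in the older strata", and items 1 and 3 leave Group 10 out. Items 5 and 6 are not matched in a comparable way. Leaving Group 10 out does not balance item 3 fully: its two pools differ in adjuvant mix.

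What is at stake is the reading of main-effect tables that go into the study report and, for the interim results, into an intended publication (SAP 5.4).

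**Working it through.** **Inputs.** Group sizes are from Protocol Table 4.2. At 18-49 there are 20 per group, with 60 in each of Groups 7 and 9. At 50 and older there are 10 per group, with 30 in each of Groups 7 and 9 and none in Group 10.

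**Step 1: reproduce the stated pool sizes.**
- High-dose adjuvanted, Groups 3+4+8+9: 30+30+30+90 = 180.
- Low-dose adjuvanted, Groups 1+2+6+7: 30+30+30+90 = 180.
- AS03, Groups 2+4+7+9: 30+30+90+90 = 240. AF03, Groups 1+3+6+8: 4 × 30 = 120.
- Unadjuvanted, Group 10: 20.

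All agree with the documents.

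**Step 2: composition.**

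| Pool | One injection | Aged ≥50 | AS03 |
|---|---|---|---|
| Each adjuvanted pool, items 5 and 6 | 60/180 = 33% | 60/180 = 33% | 120/180 = 67% |
| Group 10 | 0/20 | 0/20 | none |
| AS03, item 4 | 60/240 = 25% | 80/240 = 33% | all |
| AF03, item 4 | 60/120 = 50% | 40/120 = 33% | none |
| One-injection, item 3 | all | 40/120 = 33% | 60/120 = 50% |
| Two-injection, item 3 | none | 80/240 = 33% | 180/240 = 75% |

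Only 20+60 = 80 in each adjuvanted pool of 180 match Group 10 on age and schedule. Item 2 (dose) is balanced on age, schedule and adjuvant.

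**Step 3: do the planned safeguards remove the mismatch?**
- *Tables by age.* At 18-49 the age difference goes, but 40/120 one-injection still stands beside 0/20. At 50 and older there is no comparator. Item 4 stays at 120/160 = 75% and 40/80 = 50% two-injection at 18-49.
- *Regression.* It is optional in both documents. The protocol version includes schedule at D36. The SAP version takes D22 for Cohort 1 and D36 for Cohort 2, so it does not adjust the D36 pools.
- *Timing.* The Cohort 2 D22 sample is taken before the second injection, so the schedule problem arises at D36 and not at D22.

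**Step 4: size at D36, 18-49 table.** Let k be the two- to one-injection GMT ratio, the same for every adjuvanted formulation. It is not in the documents; I take 1, 2 and 10. The shift is the difference in schedule shares times log k.
- Items 5 and 6: factor k^(−1/3) = 1.00, 0.79, 0.46.
- Item 4, with truly equal adjuvants: AS03/AF03 = k^(0.75−0.50) = 1.00, 1.19, 1.78.
- Item 3: if the true AS03/AF03 ratio is r, the schedule ratio is multiplied by r^0.25 = 1.00, 1.19, 1.41 for r = 1, 2, 4.

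**Step 5: the shift against the contrast with Group 10.** The log10 shift is (log10 k)/3. The pool variance is SD² + (2/9)(log10 k)². The standard error of the contrast is √[pool variance/120 + SD²/20]. Coverage is from simulating 80 two-injection plus 40 one-injection participants against 20, with Welch intervals, and asking whether the interval contains the matched contrast.

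| Assumed log10 SD | k | Shift | SE | Shift/SE | 95% CI coverage |
|---|---|---|---|---|---|
| 0.5 | 1 | 0 | 0.121 | 0 | about 95% |
| 0.5 | 2 | 0.100 | 0.121 | 0.83 | about 88% |
| 0.5 | 10 | 0.333 | 0.128 | 2.60 | about 27% |
| 0.8 | 1 | 0 | 0.193 | 0 | about 95% |
| 0.8 | 2 | 0.100 | 0.194 | 0.52 | about 92% |
| 0.8 | 10 | 0.333 | 0.198 | 1.68 | about 63% |

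**Step 6: responder endpoints.** The pool reads (2/3)p₂ + (1/3)p₁. With assumed p₂ = 95% and p₁ = 90%, 50% or 10%, it reads 93%, 80% or 67%. Equal adjuvants would differ by 0.25(p₂ − p₁), about 1, 11 or 21 points.

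**The case against.** The case for leaving the plan alone has weight.

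- No hypotheses are tested, the primary objective is to describe each intervention group, and the pools are called complementary, with their make-up and sizes written out.
- Protocol 9.4.1 plans individual-arm summaries and SAP 5.1.1.4 plans them by age. Protocol 9.4.2.1 provides for GMT ratios between groups with 95% CIs. Group 8 or 9 against Group 10 at 18-49 is therefore a matched comparison that can be read from planned output.
- Dose selection applied only at the first interim (SAP 5.4), and SAP 5.7 says the formulation is no longer investigated further.
- For items 5 and 6 the error is conservative, since it understates the adjuvant effect. Every size depends on an assumed k, and with k = 1 schedule causes no distortion.

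All of this stands and limits the consequence. It does not make the pooled D36 rows a like-for-like display.

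A reader might also infer more than the documents support.

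- *That items 5 and 6 are the only route to an adjuvanted-versus-unadjuvanted comparison.* They are not: the optional regression has an adjuvant term with a none category, and the between-group ratios are a further route.
- *That the shift is 2.1 or 5.3 standard errors (k = 2 or 10, SD 0.5).* Those figures use the standard error of the pooled adjuvanted GMT alone. The effect at issue is the contrast with Group 10, whose 20 participants contribute most of the variance.
- *That AS03 was favored because of these pools.* Protocol 4.2 gives AS03 priority on prior clinical and post-marketing experience, supply readiness and regulatory experience.

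**Conclusion.** The concern holds in limited form. The D36 pooled summaries in items 4, 5 and 6 mix adjuvant with schedule. Item 3 has the corresponding imbalance in adjuvant, and the overall tables for items 5 and 6 also mix in age. The composition is exact arithmetic on the planned group sizes. The numerical effect rests on three assumptions absent from the documents: a common k, a log10 SD of 0.5 or 0.8, and the illustrative responder rates.

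At k = 2 the shift is under one standard error of the contrast. At k = 10 it is 1.68 to 2.60 standard errors, large enough to mislead. The direction is to understate the adjuvant and dose-sparing effects and to flatter AS03.

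The harm is to the interpretation of reported main-effect summaries. The documents do not support a conclusion that the study cannot evaluate the adjuvant, or that formulation selection was invalid: matched arm-level results are planned and were not displaced by these pools. It should be fixed because the remedy is cheap and schedule is a factor the sponsor itself expects to matter.

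**What to change.** Keep the prespecified pools, since redefining them after group-level unblinding would be harder to defend than adding to them. Footnote each with its one-injection and ≥50 shares. Then add the following, named in SAP 5.1.1.4 as the basis for reading these effects:

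- Overall adjuvant: Groups 8+9 aged 18-49 (N=80) against Group 10 (N=20).
- Dose-sparing: Groups 6+7 aged 18-49 (N=80) against Group 10 (N=20).
- AS03 against AF03, stratified by cohort (60 vs 60 and 180 vs 60).
- Schedule, stratified by adjuvant.

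Record the addition in SAP 5.7 as made after group-level unblinding.

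**Cost.** Table-shell and text work, plus a small loss of precision in the added rows. With equal within-arm SD, in SD units:
- Items 5 and 6: √(1/80+1/20) = 0.250 against √(1/180+1/20) = 0.236, about 6% larger.
- Items 3 and 4: the inverse-variance stratified standard error is 0.1155, from stratum variances 1/60+1/60 and 1/180+1/60. The raw value is √(1/240+1/120) = 0.1118, so it is about 3% larger.

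The matched pool of 80 is 60/80 = 75% AS03 against 67% in the raw pool. If the true AS03/AF03 ratio were 2, that alone would raise the pooled GMT by 2^(0.75−0.667) = 1.06, so the added rows should state their adjuvant mix.

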In addition to antibody response 21 days after the first injection, durability after a single injection also needs to be taken into account for schedule selection decisions, as peak immune responses after 1 injection may be adequate but could (at least theoretically) wane rapidly, potentially leaving vaccinees at risk in the event of ongoing circulation of the novel coronavirus. A further consideration is allowing sufficient time for contraction of innate immune responses and expansion of the adaptive immune response after dosing, which would be underestimated if evaluated too soon after the dose. In this regard, at least fourteen days after a second dose is deemed sufficient, based on experience with other vaccines (27) (31) (32). Therefore, antibody titers at D22 (21 days after the first injection) and D36 (14 days after a second injection) after a single injection or after 2 injections are considered relevant for informing schedule selection.

Rationale for Primary Immunogenicity Endpoint

Human experimental coronavirus infection studies have identified that the presence of pre-challenge neutralizing antibodies were predictive of protection from infection or symptoms following challenge (33) (34). For this reason, neutralizing responses are expected to provide the most relevant functional evaluation of immune responses for this vaccine candidate.

Rationale for Study Population

The study will enroll participants with no history of COVID-19 or serologic evidence of SARS-CoV-2 infection by rapid diagnostic test at the baseline visit. Inclusion of individuals with prior exposure to SARS-CoV-2 would be expected to influence immunogenicity measures. This trial is geared to identifying the dose-level of CoV2 preS dTM vaccine formulation that best supports an immune response in the naïve population, considered the population most at need for a preventive solution against SARS-CoV-2. Therefore, the immunogenicity and safety data in this study are targeted to be generated in individuals without evidence of prior exposure to SARS-CoV-2 infection.

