9.4.2 Primary Endpoints

9.4.2.1 Immunogenicity

The primary endpoints for the evaluation of immunogenicity are based on neutralizing antibody titers, which will be measured with the neutralization assay. The statistical analyses that will be performed for the following primary endpoints are as presented in [Table 3.1](#).

Pre-vaccination titers at < LLOQ will be converted to half LLOQ.

The 95% CIs for the GMTs/GMCs and GMT ratios will be calculated using normal approximation of log-transformed titers. The 95% CIs for the proportions will be based on the Clopper-Pearson method. The ratios of GMTs will be obtained between groups with the 95% CIs calculated using normal approximation of log-transformed titers. The differences in the seroconversion rates between groups will be computed along with the 2 sided 95% CIs by the Wilson-Score method without continuity correction. Additional parameters may be displayed as appropriate.

Additionally, to evaluate independent determinants of primary immunogenicity endpoints, regression models may be constructed for GMT titers and occurrence of neutralizing antibody seroconversion. When the outcome/dependent variable is a continuous numerical variable, linear models may be utilized; when the outcome/dependent variable is a categorical variable, logistic regression models may be utilized. Explanatory/independent variables inserted in these models would include age group (18-49 years, \geq 50 years), antigen dose level (low or high), and adjuvant (none, AS03, AF03). Models evaluating antibody titers or rates at D36 as the outcome variable would include also an explanatory variable corresponding to the injection schedule (1-injection, 2-injections). Multiplicative interaction terms will be included in expanded models to assess for evidence of effect modification. Non-significant interaction terms can be removed from the models.

Immunogenicity analyses will be performed on PPAS-IAS, unless otherwise specified.

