Additionally, to evaluate independent determinants of primary immunogenicity endpoints, regression models may be constructed for GMT titers and occurrence of 4-fold rise in serum neutralization titer relative to D01 at D22 for cohort 1 and D36 for cohort 2. When the outcome/dependent variable is a continuous numerical variable, linear models may be utilized; when the outcome/dependent variable is a categorical variable, logistic regression models may be utilized. Explanatory/independent variables inserted in these models would include age group (18-49 years, ≥ 50 years), antigen dose level (low-dose, high-dose), and adjuvant (none, AS03, AF03). Models evaluating antibody titers or rates at D22 for cohort 1 and D36 for cohort 2 as the outcome variable would include also an explanatory variable corresponding to the injection schedule (1-injection, 2-injections). Multiplicative interaction terms will be included in expanded models to assess for evidence of effect modification. Non-significant interaction terms with critical value < 0.05 can be removed from the models.

For descriptive purposes, the statistics presented on [Table 5.1](#) will be produced.

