5.1.2.4 Statistical Methods for Secondary Efficacy Objectives

The efficacy profile of the study vaccine candidate will be investigated with collected COVID-19 cases of efficacy endpoints including virologically-confirmed COVID-19-like illness and serologically-confirmed SARS-CoV-2 infection. Efficacy analyses will be performed on COVID-19 cases collected before receiving an authorized/approved COVID-19 vaccine. COVID-19 cases before, on and after receiving an authorized/approved COVID-19 vaccine will be listed. As the vaccine formulation used in VAT00001 is no longer investigated further and the number of COVID-19 cases collected before receiving an authorized/approved COVID-19 vaccine would be limited, planned efficacy analyses might not be performed for the final analysis.

Correlates of risk

To evaluate the correlate of risk of the collected COVID-19 cases including virologically-confirmed COVID-19-like illness and serologically-confirmed SARS-CoV-2 infection, logistic regression models will be conducted to investigate the relationship of COVID-19 cases defined above and immunogenicity responses measured by neutralization assay and ELISA. In addition, Other explanatory/independent variables under consideration are intervention groups ([vaccine, placebo]; [low-dose, high-dose, placebo]). Separate models will be performed for different consideration of intervention groups. The log10 value of neutralizing antibody titers at D36 for cohort 2 and D21 for cohort 1 are the main immunogenicity responses for this analysis. In case the majority of participants have below LLOQ neutralizing antibody titers in the placebo group, the value of below LLOQ will be treated as ½ LLOQ. Alternatively, the antibody titers of immunogenicity responses will be categorized as a discrete variable by quantile. Dose-response curve will be modeled based on the analyses in a Bayesian manner.

Vaccine efficacy

Vaccine efficacy (VE) will be assessed with the collected COVID-19 cases. The VE will be estimated as follows:

$$VE = 1 - \frac{C_v/N_v}{C_p/N_p}$$

where

- C_v and C_p are the numbers of COVID-19 cases meeting the considered secondary endpoint definition in the vaccine and placebo groups, respectively;
- N_v and N_p are the numbers of subjects in the vaccine and placebo groups, respectively.

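### The SAP's optional regression takes Cohort 1 at D22 and Cohort 2 at D36, so its injection-schedule term is fully confounded with sampling day; the protocol's model uses D36, and the change is not declared

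*SAP*

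**What the plan says.** **Protocol 9.4.2.1** offers optional regressions for neutralizing titres and seroconversion, with age group, dose level and adjuvant as explanatory variables. The schedule variable enters only for the later time point: "Models evaluating antibody titers or rates at D36 as the outcome variable would include also an explanatory variable corresponding to the injection schedule".

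**SAP 5.1.1.4** keeps the models optional: "regression models may be constructed for GMT titers and occurrence of 4-fold rise in serum neutralization titer". It keeps the same covariates and the schedule term, but attaches that term to "Models evaluating antibody titers or rates at D22 for cohort 1 and D36 for cohort 2 as the outcome variable". It has no sampling-day term. The binary outcome is now 4-fold rise, where the protocol has seroconversion.

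**Protocol 4.2**, on the choice of schedule, names D22 together with "D36 (14 days after a second injection) after a single injection or after 2 injections are considered relevant for informing schedule selection".

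**SAP 5.7**, which lists changes to the planned analyses, covers outside COVID-19 vaccination, removal of the 4-month interim analysis and possible omission of the efficacy analyses. It mentions neither the change of time point nor the change of binary outcome.

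**The concern.** The stated purpose of these models is to isolate which factors independently drive the response. A coefficient labelled as schedule should therefore reflect one injection versus two. With the SAP's time points it also carries two other differences: 21 versus 35 days since the first injection, and 21 versus 14 days since the last. A reader of the output would have no way to tell the effect of the second injection from titre kinetics after the first.

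The expanded models inherit the problem. A schedule-by-age or schedule-by-adjuvant interaction could not be told apart from kinetics after the first injection that differ by age or adjuvant.

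Choosing an injection schedule is a declared aim of the study, so the label on this coefficient matters if the model is fitted.

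**Working it through.** **Inputs.** Arm sizes: Protocol Table 4.2. Visit days and windows: Protocol Tables 1.1 and 1.2. Serum and microneutralization at D36 for all 440 participants: Protocol Table 8.1.

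**1. Reproduce the plan's group sizes (adjuvanted arms).**
- One injection: 4 × (20 + 10) = 120.
- Two injections: 2 × (20 + 10) + 2 × (60 + 30) = 240.

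Both match Protocol 9.2 and SAP 5.1.1.4. The model also has an adjuvant level of none, so the 20 unadjuvanted Cohort 2 participants enter, giving 120 + 240 + 20 = 380. This assumes that placebo is left out, because the dose covariate has only low and high levels.

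**2. Can schedule and day be separated?** A design matrix for these 380 participants was built with an intercept, age group, dose, AS03, AF03, schedule and sampling day.

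| Time points used | Columns | Rank | Schedule–day correlation |
|---|---|---|---|
| SAP: D22 in Cohort 1, D36 in Cohort 2 | 7 | 6 | 1.00 |
| Protocol: D36 in both (day constant, no day column) | 6 | 6 | not applicable |
| D22 and D36 from both cohorts, with day term | 7 | 7 | 0 |

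Under the SAP, schedule and nominal day are the same column. Under the protocol model the schedule effect is estimable at a fixed nominal day.

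**3. Do visit windows help?** No. Cohort 1's D22 visit spans D22 to D29. Cohort 2's D36 visit starts at D36 and can reach D50 if both 7-day windows are used (22 + 7 + 14 + 7). The ranges do not overlap.

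**4. What the coefficient estimates.** Write GMT1 and GMT2 for one and two injections:

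GMT2(D36)/GMT1(D22) = [GMT2(D36)/GMT1(D36)] × [GMT1(D36)/GMT1(D22)] = R × f

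This is exact for group GMTs, and for the main-effects coefficient if f is common across arms. The documents give no f, so the values below are assumptions.

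| R (D36 versus D36) | f = 0.5 | f = 0.8 | f = 1 | f = 1.5 | f = 2 |
|---|---|---|---|---|---|
| 1 | 0.5 | 0.8 | 1 | 1.5 | 2 |
| 5 | 2.5 | 4 | 5 | 7.5 | 10 |

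A noise-free regression with R = 5 and f = 0.5, 1 and 2 returned schedule ratios of 2.5, 5 and 10. Only f = 1 leaves R unchanged. The logistic model for 4-fold rise has the same confounding, but no such simple factor.

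**5. Other readings of the SAP sentence.** If one model per cohort is meant, schedule is constant within each model and cannot be estimated. If each regimen is meant to be judged after its last injection, the SAP does not say so, and the intervals still differ (21 versus 14 days).

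**The case against.** The strongest reply is that little depends on this model. Both documents make it optional, no hypotheses are tested, and no decision rule is tied to the coefficient. SAP 5.1.1.4 also firmly plans the primary endpoints at D22 and D36 by injection schedule, and Table 5.1 supplies 95% confidence intervals. A same-day D36 comparison therefore survives outside the regression. This stands, and it limits the weight of the point. The pooled summary is not a full substitute for an adjusted model, because its adjuvant mix differs: AS03 makes up 60 of 120 participants (2 × 30) with one injection and 180 of 240 (2 × 90) with two. Arm-level summaries at D36 do not have that problem.

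A second reply is that comparing each regimen after its own last injection is a legitimate question, and that Protocol 4.2 describes D22 and D36 in such terms. That is fair as far as it goes: the contrast is a different estimand, not a meaningless one. But the SAP neither names it nor declares the change.

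A reader might also infer that evidence on waning after one injection is lost. It is not. Cohort 1 titres are still summarized at D36, D181 and D366, and antibody persistence is described in SAP 5.1.3.

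Nor do the documents show that 4-fold rise is the wrong binary outcome. It is a listed primary endpoint in both, alongside seroconversion; the fault is only that the switch is undeclared.

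**Conclusion.** The point holds as an undeclared departure from the protocol that leaves the model's schedule term uninterpretable as a schedule effect. The confounding is complete by design and rests on no assumption beyond the nominal visit days. Its numerical consequence is unknown: the factor is f, and the 0.5 to 2.0 range is illustrative only.

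A reader might conclude that the choice between one and two injections would rest on a distorted estimate. The documents do not support that. The model may never be fitted, everything is descriptive, and same-day summaries by schedule are planned. SAP 5.4 confines dose selection to the first interim analysis, and SAP 5.7 says that the study formulation is no longer being pursued. The correction is worth making so that any schedule coefficient that is reported means what its label says.

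The D21 sample named for Cohort 1 in SAP 5.1.2.4 is a separate clerical correction in a different analysis and adds nothing to this point.

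**What to change.** In SAP 5.1.1.4:

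- Fit any model that contains an injection-schedule term on D36 outcomes in both cohorts, as in Protocol 9.4.2.1.
- If the D22-versus-D36 contrast is still wanted, keep it as a supportive comparison, labelled as each regimen after its last injection, and state the 21- and 14-day intervals.

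In SAP 5.7, record any departure from Protocol 9.4.2.1 that remains, including the move from seroconversion to 4-fold rise as the binary outcome, with a reason.

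The cost is SAP wording and, if the models are fitted, a rerun. No new visits or samples are needed, since D36 serum and microneutralization are planned for all 440 participants; the documents show these assays as planned, not as completed. Because both documents report that a partial database lock has already taken place, the correction should be declared as made after that lock.
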